#### 10 Missing data

11

12 Investigators will make efforts to minimize the amount of missing data including providing 13 reminders (e.g., phone calls, text messages, email) to trial subjects to complete PRO 14 instruments, monitoring compliance with PRO instrument completion throughout the assessment period, following up with trial subjects who are not successfully completing PRO 15 16 instruments (and, where permissible, close contacts if the trial subject is not responding), and 17 recording verbal responses for those who are unable to self-record because of illness or other 18 circumstances. Investigators will obtain contact information for close contacts of trial subjects for 19 use in case of nonresponse. If the investigator or a member of the study team plans to contact a 20 family member or other close contact when subjects do not respond to follow-up, this will be 21 described in the informed consent document approved by the institutional review board. The reasons for missing data will be documented. The informed consent process and informed 22 23 consent document will include information to educate prospective subjects about the continued 24 scientific importance of their follow-up data even if they choose to discontinue treatment. The 25 investigators will plan appropriate methods for handling missing data in the analyses. considering the reason for the missing data based on established guidelines. 26

2 The investigators will prospectively specify how hospitalization will be handled in the statistical analysis. If hospitalization occurs in a study participant, the investigators will determine whether 3 the hospitalization is associated with the viral infection or whether the hospitalization was 4 5 irrelevant. If the hospitalization is associated with the viral infection then the participant would 6 almost always become symptomatic before any hospitalization and hospitalization would not result in missing data with regards to the primary outcome. The hospitalization will not be 7 8 considered a form of missing data in this case. If the hospitalization is not associated with viral 9 infection such as SARS-CoV-2 infection and study participant was asymptomatic at the time of death, then the investigators will consider the specific datapoints as "missing data" that will be 10 11 determined as outlined in this section.

12

13 The investigators will prospectively specify how death will be handled in the statistical analysis. If death occurs in a study participant, the investigators will determine whether the death is 14 associated with viral infection such as SARS-CoV-2 infection or whether the death was 15 16 irrelevant. If the death is associated with SARS-CoV-2 infection then the participant would 17 almost always become symptomatic before any death and death would not result in missing data with regards to the primary outcome. The death will not be considered a form of missing 18 data in this case. If the death is not associated with SARS-CoV-2 infection and study participant 19 20 was asymptomatic at the time of death, then the investigators will consider the specific 21 datapoints as "missing data" that will be determined as outlined in this section.

22

Missing data will be handled by the mixed effects models in the analysis, which assumes that the missing data mechanism is 'missing at random'. The analysis will be redone by independent methods by analyzing only complete cases versus impute the missing data using single or multiple imputation methods. The aim of the missing data approach will be to ascertain vital status for all

- trial subjects even after a subject decides to discontinue treatment or discontinue participation in
   the trial, including follow-up for key outcomes, while adhering to informed consent requirements.
- 3
- 4

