10 Viral infection will be defined clinically based on history obtained by the investigator who is an 11 infectious diseases physician and stringent criteria will be followed. Viral infection will be defined as presence of at least two new onset independent symptoms or signs (fever) of respiratory 12 disease that cannot be attributed to bacterial cause. For example, the combination of coryza 13 14 (runny nose) and sore throat is very characteristic of a viral illness since there is no bacterial 15 "rhinitis". The combination of fever and cough is not specific enough presentation since it can be attributed also to bacterial bronchitis or pneumonia. A study participant with chronic allergies or 16 17 chronic sinusitis or asthma will not be included in the study since they may have chronic runny 18 nose or headache or cough.

19

20 **Primary** measures of efficacy (will be assessed in ALL the study participants):

21

The following **primary** outcomes are based on criteria that can be obtained reliably and consistently for all the study participants (based on history and thermometer).

24

• Development of any symptom of viral infection within 14 days after exposure (YES/No).

1	• Severity of viral illness based on a quantitative score system. Each of the above 14
2	symptoms will be given a score based on severity: 1 for mild, 2 for moderate, 3 for severe.
3	Then a total severity score will be estimated (range of score is 0-42). Common example: a
4	person with mild coryza, sore throat and cough will be given a score of 3.
5	
6	
7	Secondary measures of efficacy (will be assessed in study participants but some endpoints
8	such as diagnostic tests may not be available in all the study participants):
9	
10	The following secondary outcomes are based on either non quantitative criteria (categorical)
11	or criteria that may not be available for all the study participants (for example FDA approved
12	diagnostic tests). The study will not pay for any diagnostic tests. These diagnostic tests for
13	viruses may be available in the setting of real world setting and clinical care of each participant
14	(for example if performed by the participant or ordered by a doctor in the setting of clinical care).
15	
16	
 
Development of new onset fever (T> 100.3 F or 38C) based on documented
 

17	measurements of temperature on a daily basis throughout the duration of the study.

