#### 13 Assessment of symptom severity of viral infection (including COVID-19(

14

Assessment of symptom severity of viral infection including COVID-19 will be performed based 15 16 on the FDA guidance on Assessing COVID-19-Related Symptoms in Outpatient Adult and Adolescent Subjects in Clinical Trials of Drugs and Biological Products for COVID-1991. Patient-17 reported outcome (PRO) instruments will be used to assess COVID-19-related symptoms. 18 19 PRO assessments of COVID-19-related symptoms will be done at least every 24 hours and will 20 be conducted at the same time each day. Electronic data collection systems will be used with 21 reminders to trial subjects to complete the PRO instrument to minimize missing data and provide time stamps of completion. Alternatively, if a paper-based diary is used, the study team 22 will send reminders (e.g., phone calls, text messages, email) to trial subjects. A set of common 23 24 viral-related symptoms (see Table 1) will be included in the daily PRO assessments of all trial 25 subjects regardless of which symptoms a subject had at baseline, as new symptoms may appear following the baseline assessment. Each symptom will be scored individually using the 26

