## 6 Power/Sample Size:

7

8 The study is purely exploratory and is not powered to do a formal hypothesis testing. The data 9 from this study will set the basis for large randomized controlled clinical trials to test the safety of 10 mito-MES in the setting of treatment of viral illnesses. In addition, preliminary data will be 11 obtained on the efficacy of Mito-MES to reduce severity of viral illness. More specifically, all the proposed primary endpoints of efficacy are based on objective quantifiable criteria (fever based 12 on thermometer, duration of symptoms based on number of days, severity of viral illness based 13 14 on quantitative summary score that considers at least two independent symptoms of viral illness based on a clinically relevant definition of viral illness made by a physician). The "effect size" of 15 16 the intervention Mito-MES on these quantifiable outcomes of viral illness in humans will be 17 determined. The safety of Mito-MES in the setting of viral illness will be recorded. This is essential information for the design of larger RCT studies. 18

19

20 Based on resources, we enrolled 80 study participants.

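### No planned missing-data analysis is specified to depart from missing at random, although the plan recognises illness, the primary outcome, as a reason for not self-recording

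*Combined protocol and SAP*

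**What the plan says.** Two measures are primary (Primary measures of efficacy). One is "Development of any symptom of viral infection within 14 days after exposure (YES/No"; the other is a severity score summed over 14 symptoms, with a range of 0 to 42. Symptoms are self-reported: "PRO assessments of COVID-19-related symptoms will be done at least every 24 hours" (Assessment of symptom severity of viral infection).

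The Missing data section first lists steps to limit loss. These are reminders, contact with relatives or other close contacts, documentation of reasons, and "recording verbal responses for those who are unable to self-record because of illness or other" circumstances. It promises methods that take account of why data are missing, but does not say there what they are. Hospitalisation or death related to the infection is not treated as missing for the primary outcome.

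The methods come at the end of the section: "Missing data will be handled by the mixed effects models in the analysis, which assumes that the missing data mechanism is 'missing at random". The check on them is: "The analysis will be redone by independent methods by analyzing only complete cases versus impute the missing data using single or multiple imputation methods". No imputation model, fill-in value or missingness mechanism is given.

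The sensitivity list under Interpretation of Results/Statistical Analyses covers analysis sets, outliers, clustering, baseline adjustment and distributional assumptions. None of these varies the missing-data mechanism.

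**The concern.** Missing at random means that, given what was recorded, the chance of being missing does not depend on the unseen outcome. The plan names one route by which it could: people too ill to record, when falling ill is the outcome. Everyone enters without symptoms. A participant whose record stops before the first symptom therefore has a history with no symptoms in it, and a model using that history has no sign that this person became ill.

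The planned analyses may agree with each other because they lean on the same or a similar assumption, and that agreement could be read as robustness. What is at stake is the descriptive estimate, which is the product of this study. Power/Sample Size says the effect size and safety data are needed to design larger randomised trials, so an illness rate or severity score that is too low would carry forward.

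**Working it through.** **Inputs from the plan.** The only numerical design figure is the enrolment: "Based on resources, we enrolled 80 study participants". No alpha, power, effect size or dropout rate lies behind it, so there is nothing to reproduce. No illness rate or missing-data rate is stated. The one attrition figure (below 5%, in Dose Justification) concerns gastrointestinal discomfort at 40 mg/day in two earlier trials and does not bear on non-response through illness. All rates below are therefore assumptions.

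**Step 1: direction and size for the yes/no outcome.** Let p be the true illness rate, a the share of ill participants with no outcome, and b the share of well participants with no outcome. The expected complete-case rate is

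p(1 − a) / [p(1 − a) + (1 − p)(1 − b)].

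For p = 0.30, a = 0.20, b = 0.05: 0.24 / (0.24 + 0.665) = 0.265.

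| True rate p | a (ill) | b (well) | Expected rate | Bias (points) |
|---|---|---|---|---|
| 30% | 5% | 5% | 30.0% | 0 |
| 30% | 10% | 5% | 28.9% | −1.1 |
| 30% | 20% | 5% | 26.5% | −3.5 |
| 30% | 30% | 5% | 24.0% | −6.0 |
| 20% | 20% | 5% | 17.4% | −2.6 |
| 40% | 20% | 5% | 36.0% | −4.0 |

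If the well drop out more than the ill, the sign reverses. With p = 0.30, a = 0.05, b = 0.20: 0.285 / (0.285 + 0.56) = 0.337, or +3.7 points.

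**Step 2: effect of an earlier symptom.** One recorded symptom settles the yes/no outcome, so only ill participants who stop before any symptom is recorded are lost. Take p = 0.30, b = 0.05 and 20% of the ill stopping:
- none had recorded a symptom: a = 0.20, bias −3.5 points;
- half had: a = 0.10, bias −1.1 points;
- three quarters had: a = 0.05, bias 0.

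**Step 3: the severity score.** An earlier symptom does not protect this measure. The plan's own example scores mild coryza, sore throat and cough as 3. If that person stops responding and all three become moderate, the true score is 3 × 2 = 6, but 3 is on record. The yes/no outcome is right and the severity score is halved.

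**Step 4: what a bounding analysis would show.** For n = 80, m missing and x ill among the 80 − m observed, the bounds are x/80 and (x + m)/80. The figure of 80 is used for illustration only.

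| m | x / observed | Observed rate | All unknown well | All unknown ill |
|---|---|---|---|---|
| 4 | 23/76 | 30.3% | 28.8% | 33.8% |
| 8 | 22/72 | 30.6% | 27.5% | 37.5% |
| 12 | 20/68 | 29.4% | 25.0% | 40.0% |

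Intermediate departures can be shown by multiplying the odds of illness among the missing. With m = 8, the observed odds are 22/50 = 0.44. Doubling them gives 0.88/1.88 = 0.468, and (22 + 8 × 0.468)/80 = 32.2%. Multipliers of 4 and 8 give 33.9% and 35.3%.

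**Scale.** The exact 95% confidence interval for 24/80 is 20.3% to 41.3%.

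**The case against.** The strongest reply is that little may be missing in the end. The plan mentions illness because answers will then be taken verbally, and answers so taken are not missing. Staff take a history by telephone on days 1, 7 and 14 (Sessions by study staff), the Participant timeline table also marks a staff assessment at day 21, and close contacts can be approached. A lapsed diary can be repaired at a later call when the question is yes or no. All of this stands, and it makes a large bias in the yes/no rate less likely. It gives no analysis for those who remain missing, and it helps the severity score less, because a score recalled later or by proxy is weaker than a yes or no.

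A reader might infer that every re-analysis must assume missing at random and that none could show a bias. The documents do not support that. Single imputation could count missing as ill, multiple imputation could be delta-adjusted, and reason-based methods are left open. What can be said is that no such analysis is specified.

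A reader might also infer that the plan predicts loss of data through illness, or that the illness rate is biased low. The first reading leaves out the verbal recording. The second is conditional: nothing shows that ill participants respond less after this follow-up, and Step 1 shows that the sign can reverse.

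Finally, "The study is purely exploratory and is not powered to do a formal hypothesis testing", so no test result is at risk. That limits the consequence to the descriptive estimates.

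**Conclusion.** The point holds as a conditional gap and a cheap improvement. The main method assumes missing at random, the complete-case check does not relax it in the doubtful direction, and the unspecified imputation ordinarily shares it. If ill participants remain missing more often than well ones after all the planned follow-up, the illness rate could be too low, and the severity score more so, without the planned comparisons revealing it.

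The size cannot be derived from the documents. Under the assumed inputs with 5% missing among the well, a true 30% would appear as 28.9% to 24.0% when 10% to 30% of the ill lack an outcome. It would be unbiased if enough of them had recorded a symptom first. A shift of 3.5 points is small beside the sampling uncertainty for 24/80. Unlike sampling error, though, it would not appear in a confidence interval.

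**What to change.** In the Missing data section, replace the complete-case re-analysis as the robustness check:

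- **Yes/no outcome.** Report the rate over the intention-to-treat set of mito-MES participants twice: once with every unknown outcome counted as ill, and once with every unknown counted as not ill. Anyone with a symptom recorded before contact was lost counts as ill. Base the robustness statement on that range.
- **Denominator.** Use the same one as the primary analysis, and do not assume it is 80. The selection criteria remove participants with a positive SARS-CoV-2 test from the final analysis. They also refer to a mito-MES group, and the Participant timeline table has a drug/no-drug row, so it is not clear that all 80 took the drug. State how the exclusion affects the denominator.
- **Severity score.** Repeat the multiple imputation with imputed scores shifted upward in steps whose size and range are written down before the outcomes are analysed.
- **Complete cases.** Keep as descriptive only.

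The cost is some wording and a few lines of code. No new data, visits or participants are needed, so it remains possible although the plan describes enrolment as done. The downside is a wider and less favourable reported range when several outcomes are missing. When few are missing, the range is narrow and the robustness statement is better founded.

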### Sample Size Considerations

5

## 6 Power/Sample Size:

7

8 The study is purely exploratory and is not powered to do a formal hypothesis testing. The data 9 from this study will set the basis for large randomized controlled clinical trials to test the safety of 10 mito-MES in the setting of treatment of viral illnesses. In addition, preliminary data will be 11 obtained on the efficacy of Mito-MES to reduce severity of viral illness. More specifically, all the proposed primary endpoints of efficacy are based on objective quantifiable criteria (fever based 12 on thermometer, duration of symptoms based on number of days, severity of viral illness based 13 14 on quantitative summary score that considers at least two independent symptoms of viral illness based on a clinically relevant definition of viral illness made by a physician). The "effect size" of 15 16 the intervention Mito-MES on these quantifiable outcomes of viral illness in humans will be 17 determined. The safety of Mito-MES in the setting of viral illness will be recorded. This is essential information for the design of larger RCT studies. 18

19

20 Based on resources, we enrolled 80 study participants.

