18	Temperature will be recorded in a diary and recording temperature would be a requirement
19	for study participation.
20	• Duration of ANY of at least three respiratory/systemic symptom of viral illness in days
21	(Symptom 1: fever, Symptom 2: cough, Symptom 3: coryza, Symptom 4: sore throat,
22	Symptom 5: shortness of breath, Symptom 6: chills, Symptom 7: fatigue, Symptom 8: loss
23	of smell or taste, Symptom 9: myalgias, Symptom 10: arthralgias, Symptom 11: headache,
24	Symptom 12: nausea, Symptom 13: vomiting, Symptom 14: diarrhea

1	Confirmation of viral infection based on a FDA approved diagnostic test (for e	xample
2	respiratory panel PCR that also detects RSV and influenza or other respirator	y viruses, rapid
3	antigen test for SARS-CoV-2, PCR for SARS-CoV-2).	
4	• Symptomatic viral infection: proportion of participants with fever, cough, or oth	ner
5	respiratory/systemic symptoms (including but not limited to fatigue, loss of sm	ell or taste,
6	myalgias, arthralgias, shortness of breath, sore throat, headache, chills, coryz	a, nausea,
7	vomiting, diarrhea).	
8	Symptomatic moderate to severe viral infection. Based on established score s	system a viral
9	illness will be categorized as moderate or severe if the participant grades at le	east 2 different
10	symptoms as "moderate" or "severe".	
11	Symptomatic PCR confirmed SARS-CoV-2 infection	
12	Need for oxygen therapy (days)	
13	Hospitalization: Days of hospitalization attributable to viral disease: The media	an number of
14	days (or partial days) spent admitted to an acute care hospital	
15	Respiratory failure requiring ventilatory support attributable to viral disease: T	he median
16	number of days (or partial days) requiring (i) non-invasive or (ii) invasive venti	lation
17	Mortality (proportion of participants who die) attributable to viral disease and a	all-cause
18	mortality	
19		
20		
21	Outcome measures:	
22	Adverse events (day 7, 14): the proportion of participants exhibiting adver	se events of
23	any grade as defined using the established  grading scales for the severi	ty of adverse
24	event, such as the Toxicity Grading Scale for Healthy Adult and Adolesce	nt Volunteers

1	Enrolled in Preventive Vaccine Clinical Trials
2	https://www.fda.gov/media/73679/download).
3	
1	Design of Study:
5	Design of olday.
5	
6	Overview of study design
7	Open label clinical trial (intervention with a diet supplement) to evaluate the safety and efficacy

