## Main Parameters of Safety

,	•		
۰.	,		
	/		
4	1		

_	
3	Adverse events (day 7, 14): the proportion of participants exhibiting adverse events of
4	any grade as defined using the established  grading scales for the severity of adverse
5	event, such as the Toxicity Grading Scale for Healthy Adult and Adolescent Volunteers
6	Enrolled in Preventive Vaccine Clinical Trials
7	https://www.fda.gov/media/73679/download).
8	
9	Main Parameters of Efficacy
10	
11	Primary measures of efficacy (will be assessed in ALL the study participants):
12	
13	The following primary outcomes are based on criteria that can be obtained reliably and
14	consistently for all the study participants (based on history and thermometer).
15	
16	• Development of any symptom of viral infection within 14 days after exposure (YES/No).
17	• Severity of viral illness based on a quantitative score system. Each of the above 14
18	symptoms will be given a score based on severity: 1 for mild, 2 for moderate, 3 for severe.
19	Then a total severity score will be estimated (range of score is 0-42). Common example: a
20	person with mild coryza, sore throat and cough will be given a score of 3.
21	
22	
23	Secondary measures of efficacy (will be assessed in study participants but some endpoints
24	such as diagnostic tests may not be available in all the study participants):
25	

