### 1 Sessions by study staff

2 There are a total of 5 study visits over a period of 14 days. Day 0 is the day of exposure to

3 SARS-CoV-2.

4 Session 1 (before D0): Screening and enrollment. A medical history, study questionnaire,

5 eligibility assessment, informed consent will be performed by the investigator

6 Session 2 (before D0 or days 0-4): Dispension (allocation) of mito-MES (the study team will

7 ship overnight the compound to the study participants).

8 **Session 3 (day 1):** Telephone consult. Medication use, history (review of systems), adverse

9 event assessment, adherence diary, symptom diary, temperature diary will be assessed.

10 **Session 4 (day 7):** Telephone consult. Medication use, history (review of systems), adverse

11 event assessment, adherence diary, symptom diary, temperature diary will be assessed.

12 Session 5 (day 14): Telephone consult. Medication use, history (review of systems), adverse

13 event assessment, adherence diary, symptom diary, temperature diary will be assessed.

1	
2	Sessions by study participant
3	
4	Sessions by study participant
5	Day 1-21: Performance of diagnostic SARS-CoV-2 test in nasal swab
6	
7	Daily on D1-14
8	Adherence diary
9	Symptom diary
10	Temperature diary
11	
12	Symptom severity scores will be recorded on days 0, 1, 7, 14 by history.
13	All study visits will be remote (phone call or video visit).
14	
15	Screening
16	The following parameters will be reviewed:
17	HIV status
18	• Age
19	• Gender
20	Underlying condition and comorbidities
21	Medications
22	Pregnancy status (if applicable)
23	• Demographic characteristics: Birth sex, gender, race, ethnicity (sex will be considered as
24	a biological variable);

•	Behavioral risk factors:	Cigarette smoking	(yes or no, pack years	s), alcohol use;
---	--------------------------	-------------------	------------------------	------------------

 Clinical factors: Body-mass index (BMI), hypertension (based on self-report and medications), diabetes (based on self-report and medications), kidney disease (self-report),
 liver disease (self-report and medications), adjudicated myocardial infarction (MI)(self-report and medications), and hepatitis C virus (self-report and medications), use of hormones (e.g. testosterone or contraceptives)(self-report and medications), menopausal status (selfreport);

8

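### The sample-size section calls all primary endpoints objective and lists the wrong ones; the defined primaries are quantified participant reports taken by history in an open-label study

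*Combined protocol and SAP*

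**What the plan says.** The Power/Sample Size section states that all the "proposed primary endpoints of efficacy are based on objective quantifiable criteria". It gives three: fever by thermometer, symptom duration in days, and a severity score tied to a physician's definition of viral illness. It adds that the effect size on these outcomes will be determined and is needed to design larger randomised trials.

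Section 3.5 (Objectives) and Main Parameters of Efficacy name two primary measures: "Development of any symptom of viral infection within 14 days after exposure (YES/No") and "Severity of viral illness based on a quantitative score system", a sum over 14 symptoms. Both places say that the primary outcomes can be obtained reliably and "consistently for all the study participants (based on history and thermometer"). Documented fever and symptom duration appear there as secondary measures.

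On measurement, the section on assessing symptom severity says that patient-"reported outcome (PRO) instruments will be used to assess COVID-19-related symptoms". The list of study sessions says "Symptom severity scores will be recorded on days 0, 1, 7, 14 by history". Section 3.5 adds: "Viral infection will be defined clinically based on history obtained by the investigator who is an" infectious diseases physician. The design overview reads "Open label clinical trial (intervention with a diet supplement) to evaluate the safety and efficacy". No masked assessor or adjudicator is described anywhere.

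**The concern.** A number is not objective merely because it is a number. A participant who rates a sore throat as mild gives a report, and adding 14 such reports gives a quantified report. In an open-label study both the person reporting and the person taking the history can be influenced by knowing that the drug is being taken. The plan describes its endpoints as free of that weakness and supports the description with outcomes that are mostly not its primary ones.

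No confirmatory test is at stake, since the study disclaims formal hypothesis testing. What is at stake is the effect size. If that estimate partly reflects how symptoms were reported or attributed, later trials will be sized on it.

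**Working it through.** There is no calculation in the plan to reproduce: the sample size of 80 is set by resources, with no event rate, effect size, alpha or power. The check compares sections and adds some short arithmetic.

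**Step 1. Which endpoints are primary?**

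| Criterion | Summary | Section 3.5 and Main Parameters of Efficacy | Power/Sample Size |
|---|---|---|---|
| Illness or any symptom, yes/no | primary | primary | not listed |
| Severity score | secondary | primary | listed as primary |
| Measured fever | secondary | secondary | listed as primary |
| Symptom duration | secondary | secondary | listed as primary |

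Of the three criteria in the sample-size section, one is a defined primary in section 3.5 and none is primary in the Summary. The yes/no measure, primary everywhere else, is absent.

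**Step 2. How are the two defined primaries measured?** Table 1 has 14 items: 10 rated none to severe (0–3), 2 counted as episodes of vomiting or diarrhea (0–3), and 2 for smell and taste (0–2). All are answered by the participant. The fever item asks about feeling hot or feverish and is not a temperature reading.

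- Maximum from Table 1: 10×3 + 2×3 + 2×2 = 40.
- Maximum stated in section 3.5: 14×3 = 42.

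The two maxima need reconciling. The item lists also differ: section 3.5 separates muscle and joint pain and combines smell with taste, while Table 1 does the reverse. If measured temperature did feed the fever item, that item would still supply at most 3/42 = 7% of the score range.

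**Step 3. Who knows the treatment?** The study is open label. The study team ships the drug. The same calls on days 1, 7 and 14 review medication use, the adherence diary and the symptom diary. The Data and Safety Monitoring Plan has the physician of record evaluate all information collected. No sentence says that the assessor is unmasked, but nothing described would keep that person masked.

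**Step 4. Which way could the error go?**

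- Participants who feel protected may under-report, and an assessor may attribute symptoms to a non-viral cause. Both favour the drug.
- Nausea, vomiting and diarrhea are scored symptoms, and the dose justification and monitoring plan acknowledge gastrointestinal effects of the drug. Counting these as illness works against the drug. They are 3 of 14 symptoms, up to 9/42 = 21% of the stated score range. Their frequency at the study dose is not given.

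The net direction cannot be determined from the documents.

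**Step 5. How much misclassification would matter?** Treat the 80 as one group of independent people and assume rates of 20%, 30% and 50%, since the documents give none. The 95% half-width is 1.96 × √(p(1−p)/80):

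- p = 0.20: 8.8 points, or 0.0877×80 = 7.0 cases
- p = 0.30: 10.0 points, or 0.1004×80 = 8.0 cases
- p = 0.50: 11.0 points, or 0.1096×80 = 8.8 cases

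Each case gained or lost moves the rate by 1/80 = 1.25 points. A net change of 7 to 9 cases in either direction therefore equals the sampling error. This is a yardstick, not an estimate of how many cases would change.

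**The case against.** The open-label design is disclosed, the study calls itself purely exploratory, and the plan says that false positives will not change practice. This stands and limits the consequence to the planning estimate.

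The thermometer is a real instrument, and section 3.5 cites it for the primary outcomes. This also stands, so the primaries are mainly rather than wholly self-reported. Documented fever is nevertheless a secondary measure, and Table 1 rates fever by feeling.

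Neither primary bullet describes a case-by-case attribution step, and the inclusion criteria apply the same clinical definition to the index case. Investigator judgement of each primary case is therefore a reading of section 3.5's general definition, not a stated procedure. It is a fair reading, because the yes/no measure concerns symptoms of viral infection and section 3.5 defines that term by the investigator's history.

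A reader might infer that the plan claims protection from bias. It does not: it says objective and quantifiable in one place, and reliable and consistent in two others. A reader might also infer that the errors must favour the drug. Step 4 shows why that does not follow.

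Finally, daily diaries, measured fever and test results are already planned. That is correct, and it makes the repair cheap. It does not correct the description of the primaries.

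**Conclusion.** The point holds as one of labelling and method. Both primaries defined in section 3.5 are quantified participant reports, and the sample-size section is wrong to call them objective. Its list also contradicts the endpoint definitions: two of its three entries are secondary in section 3.5, and one of the two defined primaries is missing.

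The resulting reporting and attribution bias is of unknown size and unknown net direction. A reader might wish to express it as a false relative reduction in illness. The documents do not support such a figure. They give no illness rate and no rate of under-reporting, and possibly no comparator: the statistical section appears to disclaim a dedicated control group, while the inclusion criteria mention compared groups and the schedule has a drug/no-drug row.

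The 7-to-9-case yardstick assumes a single group of 80 with independent outcomes. Household clustering would normally widen the sampling error, and removing SARS-CoV-2-positive participants would shrink the denominator. The conclusion about the label does not depend on these assumptions.

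**What to change.** 1. In Power/Sample Size, replace *objective* with *participant-reported and quantified*. List the two primaries of section 3.5 and Main Parameters of Efficacy, and bring the Summary into line. State reporting and attribution bias as a limitation, and limit the conclusion on effect size accordingly.
2. Derive case status and severity for the primary result by a fixed, prespecified rule applied to the daily symptom and temperature diary, electronic or paper. The rule should say whether one symptom suffices or the two-symptom definition applies, which day or peak gives the severity score, and which item list and maximum (40 or 42) is used. Report investigator attribution as a sensitivity analysis with the number of cases it changes. Add a version that omits nausea, vomiting and diarrhea.
3. Show thermometer fever and available test-confirmed infection beside the primary result, each with its denominator, because tests are not paid for by the study and will be incomplete. Include the SARS-CoV-2-positive participants whom the paragraph before the exclusion criteria removes from the final analysis; otherwise the test-based comparison omits the people it is meant to show.

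The cost is wording, a short derivation program and a few extra table rows, using data already planned. The drawback is that some non-viral or drug-related symptoms will count as cases in the primary result; the sensitivity analyses in item 2 show how many.
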